The general aim of this study is the development of the optimal algorithm for the management of all adnexal masses. This can be broken down into different specific objectives: 1) to study the occurrence of complications such as rupture, torsion, or malignancy in patients with benign looking conservatively treated masses; 2) to test the published IOTA diagnostic models for predicting that a mass is malignant at first visit or benign (either on the basis of histology following surgery or by the absence of malignant features on an ultrasound scan one year after the initial visit), and to predict complications (e.g. ocurrence of malignancy and other) during long-term follow-up; 3) to investigate factors that may be related to the need for surgery during long-term follow up; 4) to study the natural history of conservatively treated benign looking masses and to establish descriptive curves of the longitudinal changes seen in parameters from conservatively managed benign tumors (e.g. change in diameter, size of any solid component, number of papillations, or color score). We hope these curves will allow us to determine if any particular growth pattern is associated with complications or malignancy

Related to these four objectives, we aim to carry out the following analyses: 1) descriptive analysis of complications overall and by participating center (anonymised) and overall Kaplan-Meier curves for the need for surgery among benign looking masses; 2) estimation of discriminatory ability of LR1 for malignancy at the initial visit using the c-index and ROC curves and for complications during long-term follow-up using the hazard ratio and c-index within the context of survival analysis; 3) survival analysis to investigate predictors of the need for surgery during long-term follow-up of non-operated masses; 4) the development of longitudinal curves of the changes seen in the characteristics of non-operated masses using longitudinal analysis techniques such as mixed models and functional linear discriminant analysis (FLDA).

Methods

Study design

International multicenter prospective observational cohort study

Eligible for inclusion

- Any woman at least 18 years old with an adnexal mass.
- Any mass with benign ultrasound morphology may be suitable for conservative management.
- Pregnant patients can be included, but their data will be analysed separately.

Exclusion Criteria

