- Cysts that are deemed to be clearly physiological and less than 3 cm in maximum diameter are not eligible for inclusion.
- Any cyst with features of malignancy is excluded from the conservative management
- The denial or withdrawal of oral informed consent

Official approval by the Ethics Committee

The multicentre project IOTA phase 5 will be submitted to the Ethics Committee of the University Hospitals Leuven as main investigating centre as well as in each participating centre. The study will be performed in accordance with generally accepted standards of Good Clinical Practice and the investigators will adhere to all applicable laws and regulations governing the conduct of clinical trials, including but not limited to the ICH Harmonized Tripartite Guidelines for Good Clinical Practice and the Declaration of Helsinki (2008).

Insurance policy

This multicentre international study is initiated by the University Hospitals Leuven, Belgium. Each participating centre outside Belgium is fully responsible for patient care within its own hospital in agreement with local laws. Each centre is also responsible for all legal aspects of patient care and for its own insurance for all matters related to this study.

Financial Support

The IOTA phase 3 project is supported by an Applied Biomedical Research grant (Toegepast Biomedisch Onderzoek, TBM) from the Flanders Institute for Scientific and Technological Research: IWT Flanders, Belgium (IWT-TBM 070706). This grant covers costs of central data collection, proteomic analysis, analysis of new tumour markers and statistical analyses. For IOTA phase 5 we received a research grant for a doctoral researcher by the Flemish Fund for Scientific Research (FWO Vlaanderen 06260, IOTA5).

There is no financial compensation for principal investigators nor patients.

Definition of benign ultrasound morphology

This is defined on the basis of subjective assessment of ultrasound findings by an experienced ultrasound examiner. Only lesions where the ultrasound examiner is certain or almost certain that the lesion is benign can be managed conservatively. The management of benign masses will be decided according to local protocols.

Number of study patients and recruitment period

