This is an observational study and therefore a sample size cannot be calculated. We aim to collect at least 3000 women with an adnexal mass and at least 1000 women with an adnexal mass managed conservatively. We plan an initial recruitment period of eighteen months. Patients will be followed up for at least 5 years, unless surgical intervention is necessary.

Follow-up

Ultrasound (and clinical) follow up will be organised by the ultrasound examiner who entered the patient into the study. Follow-up will be after 3 months (maximal range 1-4 months), 6 months (maximal range 4-8 months) and then every 12 months (maximal range 10-14 months). Although measurement of serum CA 125 levels is encouraged, it is not mandatory for inclusion in the study. If CA125 is measured it should be recorded in the study screen and preferably measured on each visit.

Duration of follow-up

A yearly analysis will be carried out in order to evaluate acute complications. The duration of follow up will be for at least 5 years and is not limited as long as the patient is compliant with the study and the study is ongoing.

Departments (e.g. radiology departments) that are not involved with clinical decision making about plans for follow up or surgery cannot participate in the full IOTA 5 study. In these centres data can be prospectively collected as an observational study. Only patients with appropriate outcome measures (i.e. follow up ultrasonography after one or more years or patients with complete details of clinical history or surgical procedures) will be included in any statistical analysis.

Collection of clinical data

Family history: Number of first degree relatives with ovarian cancer (0-...)

Medical history:	Personal history of ovarian cancer and breast cancer
	Age (years)
	Previous hysterectomy (yes/no)
	Previous oophorectomy (yes/no)
	Contraception (drop down list) (None/oral combined contraceptive
	pill/progestogen only pill/ patch/vaginal ring/Mirena coil/copper IUD)
	Hormonal therapy (yes, no).
	Is the patient currently wishing to conceive? (yes/no)
	Menopausal status (pre- or postmenopausal)
	History of subfertility? Yes/no
	History of ovarian stimulation for subfertility? Yes/no
For ALL path	ents before menopause two extra questions pop up:

Patient is currently pregnant? (No/Yes)

Patient became pregnant during the last year? (No/Yes)

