- If yes : date of first complication:

- And pop up list (you can select more than one):
 - Acute pain
 - \circ Chronic pain
 - Suspected torsion
 - o Infection
 - Haemorrhage
 - o Rupture
 - $\circ~$ Other, please specify:
- Death: date
- Death directly or indirectly relatd to adnexal mass?
- cause of death (

• Autopsy findings: specify:

Not needed for IOTA phase 5: second stage tests

Consent / information leaflet

Information leaflets are at the discretion of the participating centres. Approval of the local Ethical Committee for clinical studies is necessary.

Serum tumour markers

Serum CA 125 measurements or other tumour markers are performed locally, using a CA 125 II immunoradiometric assay

Tissue collection

Preferably the whole tumour should be removed. However, representative biopsies may be sufficient (e.g. in advanced ovarian cancer or endometrioma).

Tumour classification

Tumours are classified according to the criteria recommended by the International Federation of Gynecology and Obstetrics (FIGO). In malignant tumours the degree of differentiation is included.

Statistical analysis

For the first objective, a descriptive analysis of complications on all data and stratified for participating center (anonymized) will be performed, as well as an overall Kaplan-Meier curve of 'complication free survival'. Complication free survival is defined as the time to the need for surgery during long-term follow-up. Patients that did not need surgery at the end of the follow-up period are right censored at the time of the last examination.

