For the second objective, the discriminatory ability of LR1 and the polytomous model to detect malignancy at the initial visit will be assessed. To this end, the logit of the risk of malignancy given by LR1, logit(LR1), is used to predict malignancy using logistic regression, and the performance assessed with the odds ratio, the c-index and a ROC curve. Linearity of the effect of logit(LR1) will be assessed using spline functions. This analysis is planned one year after the end of the inclusion phase of the trial. Non-operated masses will be classified as benign at the initial visit if there is an absence of a clinical diagnosis of cancer after 1 year of follow up. In addition, the ability of LR1 to predict complications during long-term follow-up will be assessed. This will be done using Cox proportional hazards regression with the logit(LR1) as predictor of complication free survival. Performance will be assessed using the hazard ratio and the c-index within the context of survival analysis. Linearity of the effect of logit(LR1) will be investigated using Schoenfeld residuals.

For the third objective, a multivariable survival analysis will be undertaken using Cox proportional hazards regression or more complex alternatives based on support vector machines (30). The models will be penalized to prevent overfitting, given that not enough events (i.e., patients that need surgery during long term follow-up) are expected for the number of available predictor variables. Internal validation will be assessed through bootstrapping rather than a split of the data in training and test sets (31).

For the fourth objective, longitudinal normative curves will be derived of the changes seen in the characteristics of non-operated masses. Longitudinal analysis techniques such as mixed models, longitudinal support vector machines, and functional linear discriminant analysis (FLDA) (32-34).

Study supervision

Central supervision: the Steering Committee is responsible for the protocol, quality control, interim analyses of the data and final analysis and reporting of the study.

Local supervision: the Principal Investigators are responsible for the data collection in their centres.

[name] is responsible for the co-ordination of the overall IOTA project and the contact between the centres.

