IOTA5 interim analysis

Statistical Analysis Plan

Page 2-11: Follow-up study (27 December 2017)

Page 12-19: Performance of models for ovarian tumor diagnosis when applied to all patients (operated or conservatively followed) (28 May 2019)

IOTA5 interim analysis

Follow-up study

Statistical Analysis Plan

27 December 2017

1.1 Data:

The IOTA5 database will be used for the analysis and the following in- and exclusion criteria will be used.

Inclusion criteria:

- Initial policy is conservative management,
- The mass was diagnosed as benign at the first visit (i.e. subjective assessment = benign AND certainty = certainly benign OR probably benign).
- First scan between 1 January 2012 and 1 March 2015.

Exclusion criteria:

- Patients who did not give consent; data from patients who withdrew consent during the study will not be used either
- Younger than 18 years at first scan
- Cysts that are deemed clearly physiological and less than 3 cm in maximum diameter are not eligible for inclusion. [*We identified 13 such patients in the database for the interim analysis.*]

Further issues regarding data:

- Patients who underwent surgery for the adnexal mass after the first scan, despite the initial policy being conservative management, will be used in descriptive statistics but not in the main survival analysis. We will include them in a sensitivity analysis (cf below).
- Patients who withdrew consent during the study will not be used
- Only the dominant mass of the patient will be included
- We include follow-up data up to 30th of June 2017 such that all patients should have been followed up for 24 months (protocol allows +/- 2 months, hence this date allows 26 months follow-up for all patients; for the survival analysis, we use all available data (i.e. also information on the first scan after 26 months if available) but only show results up to 30 months. 30 months implies 2.5 years, this is convenient when constructing plots. Follow-up after 30 months is incomplete and hence results are uncertain.
- Although the aim of IOTA5 was to recruit patients consecutively and organize follow-up, there is a lot of heterogeneity among centers regarding adherence to the follow-up protocol. Therefore, we will perform a sensitivity analysis including all centers that have contributed to patient recruitment. However, only data of the following centers will be used for the primary analysis (centers with sufficient data quality: based on N recruited for conservative

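### The linearity check for logit(LR1) in the Cox model uses Schoenfeld residuals, which assess proportional hazards rather than the shape of an effect

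*Protocol*

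**What the plan says.** The second objective in the protocol's Statistical analysis section has two parts, both with logit(LR1) as predictor.

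- **Logistic model, malignancy at the initial visit.** The linearity check is: "Linearity of the effect of logit(LR1) will be assessed using spline functions".
- **Cox model, complication free survival.** The linearity check is: "Linearity of the effect of logit(LR1) will be investigated using Schoenfeld residuals". No other check of functional form is named for this model, and proportional hazards is not named as something to be checked.

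For the Cox part, "Performance will be assessed using the hazard ratio and the c-index within the context of survival analysis". The Objectives section promises the same two measures: "for complications during long-term follow-up using the hazard ratio and c-index within the context of survival analysis". The event is set under the first objective: "Complication free survival is defined as the time to the need for surgery during long-term follow-up".

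The SAP is headed "IOTA5 interim analysis". Its follow-up part (section 1.2.2) uses competing-risk cumulative incidence, without a Cox model of logit(LR1). The model list in its performance part (section 1.4) includes LR2 but not LR1. The SAP therefore neither corrects nor confirms the protocol sentence.

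**The concern.** The diagnostic does not match its stated purpose. Schoenfeld residuals are examined against time and show whether a coefficient drifts during follow-up. The shape of a covariate's effect needs another tool, such as splines or martingale residuals.

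One hazard ratio per unit of logit(LR1) is a fair summary only if the log hazard is roughly linear in logit(LR1). That cannot be taken for granted here. LR1 was built to predict malignancy, whereas the event is need for surgery for any reason. The cohort is also restricted: "Only lesions where the ultrasound examiner is certain or almost certain that the lesion is benign can be managed conservatively". If the risk of surgery is flat over most of the range and rises only at the upper end, or levels off, a single hazard ratio averages over different slopes. The planned check would usually give no warning.

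**Working it through.** **1. What the residual measures.** At event time t_k the Schoenfeld residual is r_k = x_k − x̄(t_k), where x̄(t_k) = Σ x_j exp(βx_j) / Σ exp(βx_j) over those still at risk. After scaling, its expected value plus β approximates β(t_k). A trend over time therefore indicates a time-varying coefficient. Curvature in x enters only indirectly: as high-risk women leave the risk set, the best-fitting straight slope can shift.

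**2. The two readings of the sentence.**

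| Reading | Linearity check | Proportional hazards check |
|---|---|---|
| Literal | Named, but unsuitable | None named |
| Slip for proportional hazards | None named | Suitable |

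On either reading the Cox model has no suitable linearity check. This step establishes the point without simulation.

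**3. How much the check would miss (illustrative).** The protocol gives no figure to reproduce.

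Inputs from the protocol's section on number of patients and recruitment:
- Cohort: "at least 1000 women with an adnexal mass managed conservatively", so n = 1000 is the stated minimum.
- Follow-up: at least 5 years (60 months) with 18 months' recruitment. A common cut-off, which is assumed, gives 60 to 60 + 18 = 78 months.

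Assumptions not in the documents:
- Standard-normal logit(LR1).
- Exponential loss to follow-up with mean 200 months.
- Event fractions of 8, 15 and 30%, or about 80, 150 and 300 events.
- The effect shapes in the table.

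Each cell used 500 replicates, so the Monte Carlo standard error is at most √(0.25/500) = 2.2 percentage points. Tests at the 5% level:
- (a) correlation of Schoenfeld residuals with ranked event time;
- (b) score test for x times centred ranked event time;
- (c) 2-df likelihood-ratio test of a 4-knot restricted cubic spline against linear.

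Percentage flagged at about 80/150/300 events, with hazard ratios (HR) per SD except for the threshold shapes:

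| True shape | (a) Correlation | (b) Score | (c) Spline |
|---|---|---|---|
| Linear, HR 2 | 5/3/4 | 6/3/4 | 4/5/2 |
| Flat then rising, HR exp(1.0) = 2.72 above mean | 6/6/12 | 12/12/19 | 55/86/99 |
| Rising then flat, HR 2.72 below mean | 6/5/8 | 2/2/3 | 57/79/99 |
| Threshold at +1 SD, HR 4 | 5/4/7 | 8/8/13 | 42/72/98 |
| Quadratic 0.5x + 0.3x² | 7/17/37 | 21/33/55 | 97/100/100 |
| Flat then rising, HR exp(0.5) = 1.65 | 4/4/5 | 6/5/7 | 19/34/60 |
| Flat then rising, HR exp(0.4) = 1.49 | 5/5/5 | 7/8/8 | 14/24/41 |
| Rising then flat, HR 1.65 | 6/4/4 | 4/3/2 | 22/31/60 |
| Threshold at +1 SD, HR 2 | 4/5/5 | 5/7/6 | 17/24/53 |
| Quadratic 0.25x + 0.15x² | 4/5/7 | 10/10/14 | 49/68/93 |

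The exception to usually missing curvature is the strong quadratic at 300 events, where the score version flags 55%.

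**4. What the single hazard ratio would report.** For flat then rising, the fitted HR per SD was 2.01/1.98/1.91 when the truth is 1.00 below the mean and 2.72 above. It was 1.35/1.35/1.34 when the truth is 1.00 and 1.65.

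**5. A second set-up.** This used uniform censoring at 2–5 years, a 3-knot spline, 10% or 20% events and 200 runs. Under non-linear but proportional hazards (the strong flat-then-rising shape and a U-shape), the correlation version flagged 4.0–6.0% and the spline 78.5–100%. Under linear but non-proportional hazards, the correlation version flagged 98.5–100% and the spline 32–54%.

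**The case against.** - **It is probably a slip.** The tool named is the standard proportional-hazards check, and splines are named correctly for the same predictor a few lines earlier. That is plausible, but the spline sentence belongs to the initial-visit logistic model and does not carry over to the Cox model.
- **The plans have moved on.** Neither part of the SAP takes LR1 forward. This makes the practical impact uncertain. Both parts are interim plans, however, and do not withdraw the Cox analysis.
- **The cohort is larger than 1000.** The presumed-diagnosis table in SAP section 1.2.2 implies about 1470/0.47 ≈ 3,130 masses. At n = 3,100 with the same event fractions, two reruns flagged between 4% and 41% of the monotone shapes tried with Schoenfeld tests, against 83–100% with the spline. The 41% is the score version for the strong flat-then-rising shape at about 945 events; weak flat-then-rising stayed at 4–8%. The rates in the table are therefore specific to n = 1000, but the ordering holds.
- **The simulation is stylised.** The protocol prescribes no 5% test, and the simulation omits spontaneous resolution, which the SAP treats as a competing event. Both criticisms stand, so the figures are illustrative only.
- **The consequence is small.** The hazard ratio is a descriptive performance measure in an observational cohort. This stands and limits the weight of the point, although the text remains wrong as written.

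**Conclusion.** The concern holds. The named diagnostic does not assess linearity, and nothing in the protocol or SAP supplies a check that does for this Cox model. This follows from what the residual measures and does not depend on the simulation.

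The size is modest. With n = 1000 and about 80 to 300 events, Schoenfeld tests flagged 2–19% of strong and 2–8% of weak monotone shapes, against 42–99% and 14–60% for the spline. These rates depend on the assumed shapes, effect strengths, event counts and version of the test.

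The consequence is confined to the hazard ratio in the Cox part of objective 2. With a single predictor the c-index depends on ranks, so monotone curvature leaves it unchanged; a non-monotone effect would alter it. The correction should be made, but it does not threaten the study's conclusions as a whole.

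**What to change.** Replace the protocol sentence with wording such as:

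> *In the Cox model, the functional form of logit(LR1) will be examined with restricted cubic splines, as in the logistic model; proportional hazards will be examined with scaled Schoenfeld residuals.*

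If non-linearity is seen, show the spline curve with its confidence band alongside the prespecified hazard ratio and c-index, not in place of them. If hazards are non-proportional, also report how the hazard ratio changes over time. If an amendment through every centre's ethics committee is not wanted for one sentence, the same text can go into a SAP for the final analysis.

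The cost is one sentence and one extra model fit, with no new data. Two cautions apply:

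- A non-significant spline test does not prove linearity. With n = 1000 and about 80 events it detected 42–57% of the strong monotone shapes and 14–22% of the weak ones, so the curve and band should be shown rather than the test alone.
- A significant spline test is not specific to curvature. It flagged 32–54% of runs with a linear effect but non-proportional hazards, so the two checks should be read together.

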In this international multicentre study IOTA phase 5 we aim to develop the optimal evidence-based algorithm for the management of all adnexal tumours in order to improve the detection of ovarian cancer while at the same time reducing the number of unnecessary operations. At least three thousand patients with an adnexal mass will undergo an ultrasound examination and if no operation is needed they will be followed up for at least 5 years. At each visit the investigator will assess the tumour and decide whether surgery is necessary based on the available information and local protocols. Survival and logistic regression analysis will be used to develop decision aids to assist clinicians in making decisions regarding surgery and follow up.

Relation with other IOTA studies

The **IOTA study (International Ovarian Tumour Analysis)** is a multicentre collaborative project for the pre-operative characterisation of ovarian tumours..

IOTA phase 1: The **first phase** of IOTA was conducted between 1999 and 2002. Several new mathematical models were developed based on the prospectively collected data of 1066 patients with a persisting adnexal tumour from 9 European centres (1). Between 2002 and 2005 three centres continued the prospective collection in order to be able to perform an internal validation of mathematical models developed in IOTA phase 1. In this so-called IOTA **phase 1b** study a dataset of 507 new patients was prospectively collected in 3 out of the 9 original IOTA centres (2). All models proved to perform excellently with areas under the ROC curves of more than 0.94.

IOTA phase 2: The **second phase** of IOTA consisted of an external validation of the models and this was conducted between 2005 and 2007. The diagnostic algorithms were prospectively validated on 1938 patients with adnexal tumours in 19 centres in Belgium, Italy, UK, Sweden, Poland, Czech Republic, Canada, and China (3). A first analysis showed that overall performance of the logistic regression models was excellent (area under the ROC curve 0.94). We concluded that a subgroup of "uncertain" tumours needs a reliable second stage test in order to help even experienced ultrasound examiners.

IOTA phase 3: The third phase of the IOTA study started in 2010.

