- 'Ovarian crescent sign', defined as the presence of normal ovarian tissue adjacent to an adnexal tumour. ("absent" or "present", mandatory new variable for phase 3 and 5)
- Ultrasound evidence of metastases (e.g. "omental cake" or peritoneal tumoural implants). ("absent" or "present", mandatory new variable for phase 3 and 5)

Colour Doppler imaging and blood flow indices

Subsequently, the entire tumor is surveyed by CDI. The power, gain and pulse repetition frequency are initially adjusted for maximum sensitivity of low blood flow states. The lowest velocity signals are filtered out by gradually increasing the pulse repetition frequency and flow analysis is concentrated on the highest velocity signals. A subjective semiquantitative assessment of the amount of blood flow (area and colour scale) within the septa, cyst walls, or solid tumor areas is made: a score of 1 is given when no blood flow can be found in the lesion; a score of 2 is given when only a small amount of flow can be detected; 3 is given when moderate flow is present and 4 is given when the adnexal mass appears highly vascular with marked blood flow using colour Doppler (abundant flow). This colour score refers only to the colour Doppler image and not to Doppler shift spectrum. It is given for the tumour as a whole (not for a solid part or a septum only, but for the whole tumour). Multiple photographic prints are made of relevant structures and Doppler signals.

Quality control

Several informative images or volumes of all adnexal masses should be made. Preferably, these are stored digitally. Photographs or video are acceptable as well.

Subjective assessment

After ultrasonographic examination of the mass the investigator gives his subjective assessment of the mass:

A: Malignant or benign or borderline?

B: Probability of malignancy:	1 = benign
(=level of certainty)	2 = probably benign
	3 = uncertain
	4 = probably malignant
	5 = malignant
a a 10 · · · · · ·	

C: Self impression: presumed histological diagnosis (e.g. dermoid, serous cystadenoma, endometrioma, abscess...)

Surgical intervention

Surgery is performed according to local protocols. The reason for surgery, e.g. symptoms (pain, discomfort or pressure symptoms), raised serum CA125 levels or changes in the morphology or volume of the mass is recorded in the study screen.

Study screen

An astraia study screen will be used which will permit the entry of multiple scans per patient.

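### No centre effect or between-centre check is planned for the model of need for surgery, although surgery follows local protocols, so its performance in a new centre is unassessed

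*Protocol*

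**What the plan says.** The Protocol's Statistical analysis section states, for the third objective, that "a multivariable survival analysis will be undertaken using Cox proportional hazards regression or more complex alternatives based on support vector machines". The models are to be penalised, "given that not enough events (i.e., patients that need surgery during long term follow-up) are expected for the number of available predictor variables". The only validation named is: "Internal validation will be assessed through bootstrapping rather than a split of the data in training and test sets". The section does not give the resampling unit, the number of resamples or the performance measures for this objective. The c-index is named under objective 2 only.

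The modelled event depends on local practice. Under Surgical intervention: "Surgery is performed according to local protocols". Under Definition of benign ultrasound morphology: "The management of benign masses will be decided according to local protocols". The intended product is stated in the opening summary: "Survival and logistic regression analysis will be used to develop decision aids to assist clinicians in making decisions regarding surgery and follow up".

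In the Protocol's analysis section, centre appears only in the descriptive analysis of complications for objective 1, which "stratified for participating center (anonymized) will be performed". Neither part of the SAP covers objective 3. The 2017 Follow-up study part estimates cumulative incidences, with a sensitivity analysis over all centres. The 2019 part evaluates existing diagnostic models and subjective assessment. Its sections 1.5.3 to 1.5.5 allow for centre in discrimination, calibration and net benefit, mostly by random-effects pooling of centre-specific results.

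**The concern.** Bootstrapping within the development data corrects for overfitting to a finite sample. It does not show how a model behaves in a centre that contributed no patients. That gap matters more than usual here, because the event is a decision taken under each centre's own rules. Two centres with identical patients may operate at different rates. A predictor may also carry centre information: SAP section 1.5.1 says that local protocols made some centres more committed than others to measuring CA125.

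A centre adopting a decision aid would rely on its absolute predictions as well as its ranking. If surgery rates differ between centres and the model has no centre term, predictions in a new centre could be too high or too low, and the planned validation would give no sign of it.

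**Working it through.** **Figure to reproduce.** There is none. The Protocol says a sample size cannot be calculated, and it gives no event count or expected c-index for objective 3. Neither document gives a between-centre variance. What follows is an illustration over an assumed range.

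**Inputs from the documents.** At least 1000 conservatively managed women (Protocol, Number of study patients and recruitment period); 19 centres (SAP, Follow-up study, section 1.1); a penalised Cox model.

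**Assumed inputs.** 1000 + 19 × 5 = 1,095 women per dataset; 15 predictors, five of them active with log hazard ratios 0.5, 0.4, 0.3, 0.2 and 0.2; baseline hazard 0.035 per year; censoring uniform between 1 and 5 years; a fixed ridge penalty; 25 datasets per scenario; 20 bootstrap samples each; 15 new centres of 800 women each.

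**Formulas.**
- Corrected c = apparent c − mean of (c in the bootstrap sample − c of that same model in the full data). With no centre differences: 0.714 − 0.030 = 0.684.
- O/E in a new centre = observed surgeries ÷ Σ H0(tᵢ)·exp(xᵢβ), with H0 the Breslow estimate from the development data.

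| Assumed centre differences | Events | Corrected c, resampling women | Corrected c, resampling centres | Mean c in new centres | Women minus new | O/E, 10th–90th percentile |
|---|---|---|---|---|---|---|
| None | 137 | 0.684 | 0.686 | 0.688 | −0.004 | 0.86–1.09 |
| Log hazard SD 0.5 | 141 | 0.673 | 0.673 | 0.682 | −0.009 | 0.56–1.66 |
| Log hazard SD 1.0 | 171 | 0.681 | 0.682 | 0.685 | −0.004 | 0.28–2.66 |
| SD 0.5, effect SD 0.2 | 154 | 0.684 | 0.681 | 0.679 | +0.005 | 0.53–1.71 |
| SD 1.0, case-mix SD 0.5 | 184 | 0.712 | 0.700 | 0.672 | +0.040 | 0.25–2.40 |
| SD 1.0, effect SD 0.2, case-mix SD 0.5 | 193 | 0.710 | 0.693 | 0.676 | +0.034 | 0.27–2.66 |

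Monte Carlo error on the c-index is roughly 0.005–0.01, so the first four differences are indistinguishable from zero.

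**Plausibility of the O/E spread.** If a centre multiplies the hazard by exp(a), with a normal and SD s, O/E should span about exp(±1.28s). For s = 0.5 this is 0.53–1.90, a ratio of 3.6. For s = 1.0 it is 0.28–3.60, a ratio of 12.9. The simulated ratios are 1.66/0.56 = 3.0 and 2.66/0.28 = 9.5. They are somewhat narrower, as expected when percentiles are taken over only 15 centres per dataset.

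**Why rate differences alone leave c unchanged.** A constant multiplier on a centre's hazard does not alter the ranking of women within that centre.

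**Why case mix matters.** The squared effects sum to 0.25 + 0.16 + 0.09 + 0.04 + 0.04 = 0.58, so the linear predictor has SD √0.58 = 0.76 within a centre. Case-mix SD 0.5 adds 0.25 × 0.58 = 0.145 between centres, giving a pooled SD of √0.725 = 0.85. The bootstrap c is pooled over centres and gains from that wider spread; a single new centre does not. Part of the 0.03–0.04 is therefore a difference in what is being measured rather than failure of the coefficients.

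**Why the resampling unit matters.** In the two case-mix scenarios, resampling centres instead of women lowered the corrected c by 0.712 − 0.700 = 0.012 and 0.710 − 0.693 = 0.017. That closes some of the gap to the new-centre values, but not all of it.

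**The case against.** The quoted sentence is not an error in itself. It calls the step internal validation, and a random split would draw on the same centres and would not test transport either. The Protocol's Objectives section frames objective 3 as investigating factors related to surgery. Its account of earlier IOTA phases shows a programme that develops models first and validates them externally later. The two SAP parts are interim analyses and were not written for this objective.

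A reader might go further and infer that the bootstrap c-index will be too high in any new centre. The documents do not support that. They give no between-centre variance, and the table shows no inflation from differences in surgery rate alone. The bootstrap value exceeded the new-centre value in 46%, 41%, 46%, 51%, 83% and 68% of new centres, in row order. It is likewise only an inference that women, rather than centres, will be resampled.

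Nor should every spread of O/E across small left-out centres be read as miscalibration. If, say, 120 surgeries fell over the 17 main centres of the 2019 SAP part, the mean would be 120/17 = 7.1 per centre. Poisson 10th and 90th percentiles of 4 and 11 then give O/E of 0.57–1.56 from counting alone. The table avoids most of this by using 800 women per new centre.

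The study may also exceed its minimum of 1000. The SAP's presumed-diagnosis table implies 1470/0.47, about 3,100 women, if that is the relevant denominator. More women would reduce overfitting and counting noise, but not the variance between centres.

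These points limit what can be claimed. They do not close the gap: neither document names a later external validation of this model, and the Protocol's summary gives decision aids as the purpose.

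**Conclusion.** The point holds in limited form. For the objective 3 model, performance in a new centre is unassessed, because neither document plans a centre effect or a between-centre check and the event follows local practice.

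The more predictable risk is miscalibrated absolute risk. Under assumed log-hazard SDs of 0.5 and 1.0, the 10th to 90th percentile of O/E widens from 0.86–1.09 to 0.56–1.66 and 0.28–2.66. The c-index may also be overstated by about 0.03–0.04, but only if case mix differs between centres as well.

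All sizes rest on the assumed effects, event rate and between-centre SDs listed above. The absence of a between-centre check rests on the documents alone. The plan should be changed, since a better method is available at little cost.

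**What to change.** Keep the bootstrap for optimism correction and state its resampling unit, the number of resamples and the performance measures.

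Add internal-external validation by centre. Leave out each centre in turn, with small ones grouped, and refit every step including the choice of penalty. Pool the left-out c-index, calibration slope and O/E by random effects, and report the between-centre spread. This carries the SAP's by-centre approach for the existing diagnostic models over to the new one.

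Account for centre in the Cox model with a frailty term. Alternatively, stratify by centre to estimate the coefficients and state which baseline hazard applies to a left-out centre. A stratified model supplies none for that centre, so O/E cannot be computed without this choice.

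The cost is protocol or SAP wording plus one refit, with penalty tuning, per left-out centre or group: at most 17 or 19 on the SAP's centre lists, and more if support vector machine alternatives are compared. No new data are needed. Slopes and O/E from centres with few events will be imprecise, and the reported performance may look less favourable.
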